11.0 Safety Analysis

11.1 General Considerations

All safety analyses will be performed on the safety dataset. Unless otherwise specified, treatment group differences in safety parameters are evaluated using two-sided test at the significance level of 0.050. When statistical tests are performed, the comparisons will be between each ABBV-8E12 dose and placebo. With the exception of adverse events, all safety assessments that are taken no more than 45 days after the last dose of study drug infusion will be included in the safety evaluation of the Double-blind Treatment Period. All safety assessments that are taken more than 45 days but no more than 20 weeks after the last dose of study drug infusion will be included in the safety evaluation for the Post-Treatment Follow-Up Period.

11.2 Analysis of Adverse Events

All adverse events will be coded using the most current version of the Medical Dictionary for Regulatory Activities (MedDRA). A treatment-emergent adverse event (TEAE) is defined as any adverse event that begins or worsens in severity on or after the first study drug dose date and no more than 20 weeks after the last study drug dose date.

11.2.1 Adverse Event Overview

The number and percentage of subjects experiencing one or more adverse events in the following adverse event categories will be summarized for each treatment group, ABBV-8E12 Overall. No comparisons of treatment groups will be performed.

- Any TEAE
- Any TEAE that was rated as having reasonable possibility of being related to study drug by the investigator
- Any severe TEAE
- Any serious TEAE
- Any TEAE that led to discontinuation of study drug
- Any fatal TEAE

- All deaths

11.2.2 Adverse Event Incidence

Treatment emergent adverse event (TEAE) incidence will be summarized and presented using primary MedDRA system organ classes (SOCs) and preferred terms (PTs). The system organ classes will be presented in the alphabetical order and the preferred terms will be presented in the alphabetical order within each system organ class. Subjects reporting more than one adverse event for a given MedDRA PT will be counted only once for that term. Subjects reporting more than one adverse event within a SOC will be counted only once for the SOC total. Subjects reporting more than one adverse event will be counted only once in the overall adverse event total.

The number and percentage of subjects experiencing one or more TEAEs will be summarized by PT for each treatment group, ABBV-8E12 Overall. The PTs will be presented by decreasing frequency in ABBV-8E12 Overall.

The number and percentage of subjects experiencing one or more adverse events in the following adverse event categories will be summarized by primary SOC and PT for each treatment group, ABBV-8E12 Overall. No comparisons of treatment groups will be performed.

- Any TEAE
- Any serious TEAE
- Any TEAE that led to discontinuation of study drug
- Any TEAE assessed by the investigator to have Reasonable Possibility of Being Related to study drug

The number of subjects experiencing one or more TEAEs will also be summarized by maximum severity category (mild, moderate, severe and unknown) and primary SOC and PT for each treatment group, ABBV-8E12 Overall. Subjects reporting more than one TEAE for a given PT will be counted only once for that term in the most severe

category reported. If a subject has an adverse event with unknown severity, then the subject will be counted in the severity category of "unknown" unless the subject has another occurrence of the same adverse event with the most extreme severity — "Severe." In this case, the subject will be counted under the "Severe" category. No comparisons of treatment groups will be performed.

The number of subjects experiencing one or more TEAEs will also be summarized by maximum relationship category (Reasonable Possibility of Being Related, No Reasonable Possibility of Being Related and Unknown), as assessed by the investigator, and primary SOC and PT for each treatment group, ABBV-8E12 Overall. Subjects reporting more than one TEAE for a given PT will be counted only once for that term in the most related category reported. If a subject has an adverse event with unknown relationship, then the subject will be counted in the relationship category of "unknown," unless the subject has another occurrence of the same adverse event with a relationship assessment of "Reasonable Possibility of Being Related." In this case, the subject will be counted under the "Reasonable Possibility of Being Related." No comparisons between treatment groups will be performed.

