4.0 Study Objectives

The primary objectives of this study are:

- To assess the efficacy of ABBV-8E12 in slowing disease progression (cognitive and functional impairment) in subjects with Early AD as measured by the Clinical Dementia Rating-Sum of Boxes (CDR-SB).
- To assess the long-term safety of ABBV-8E12 for up to 96 weeks in subjects with Early AD.

The secondary objectives of this study are:

- To assess the pharmacokinetics of ABBV-8E12 in subjects with Early AD.
- To assess the efficacy of ABBV-8E12 in slowing cognitive and functional impairment in subjects with Early AD as measured by the Mini-Mental State Examination (MMSE), Alzheimer's Disease Assessment Scale (14-Item) Cognition Portion (ADAS-Cog-14), Repeatable Battery for Assessment of Neuropsychological Status (RBANS), 24-Item Alzheimer's Disease Cooperative Study/Activities of Daily Living Scale Adapted for Patients with Mild Cognitive Impairment (ADCS-MCI-ADL-24), Functional Activities Questionnaire (FAQ), University of California San Diego Performance Based Skills Assessment, Brief Version (UPSA-Brief), and Neuropsychiatric Inventory (NPI).
- To assess the global impact of ABBV-8E12 on cognition, function and behavior as measured by Alzheimer's Disease Cooperative Study Clinical Global Impression of Change for Mild Cognitive Impairment (ADCS-CGIC-MCI).

The exploratory objectives of this study are:

- To assess the effect of ABBV-8E12 on CSF and plasma tau protein.
- To assess the effect of ABBV-8E12 on potential CSF and plasma biomarkers of disease progression.

- To assess the efficacy of ABBV-8E12 in slowing the rate of regional and/or whole brain atrophy in subjects with Early AD as measured by volumetric magnetic resonance imaging (vMRI).
- To assess any signals or trends for efficacy of ABBV-8E12 in removing tau deposits or slowing the accumulation and spread of tau deposits in the brain as measured by tau positron emission tomography (PET) in a subset of subjects
- To generate additional data for the correlation between retinal amyloid imaging and amyloid PET imaging in a subset of subjects.
- To characterize the performance of a digital clock drawing test (dCDT) in measuring cognitive function and assess its correlation with other clinical rating scales and biomarkers in a subset of subjects.

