8.1.6 Safety Analyses

All safety analysis will be performed on the safety data set unless otherwise specified. Comparisons between each ABBV-8E12 dose group and placebo will be performed with two-sided test at the significance level of 0.05, if applicable. Pairwise comparisons for each ABBV-8E12 dose group versus placebo will be evaluated.

All safety assessments that are taken no more than 20 weeks after the last dose of study drug will be included in the safety evaluation for subjects who complete the double-blind Treatment Period or PD and do not roll over to the planned extension study. If subjects enroll in the planned extension study, their safety information collected before the first dose of the planned extension study will be included in the safety evaluation for the double-blinded period.

Study Drug Exposure and Compliance

The number of doses on study drug will be summarized by treatment group and all treatment groups combined. The number and percentage of subjects with at least 90% compliance with study drug (i.e., complete 90% of scheduled doses) will be summarized by treatment group and all treatment groups combined.

Adverse Events

A treatment-emergent adverse event (TEAE) is defined as any adverse event that begins or worsens in severity on or after the first study drug dose date and no more than 20 weeks after the last study drug dose date.

Unless otherwise specified, the treatment group differences in continuous safety variables (e.g., change from baseline to final observation on laboratory tests) will be assessed using an ANOVA model with the term of treatment, and the treatment group differences in binary safety variables will be evaluated using a Fisher's exact test.

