8.1.6.1 Analysis of Adverse Events

Adverse events will be coded using the most current version of the Medical Dictionary for Regulatory Activities (MedDRA). The number and percentage of subjects who report TEAEs will be tabulated by MedDRA system organ class (SOC) and preferred term (PT) for each treatment group, overall ABBV-8E12 and all treatment groups combined. Treatment group differences between each ABBV-8E12 dose group and placebo will be analyzed using Fisher's exact test.

The number and percent of subjects experiencing treatment-emergent SAEs (including deaths) and adverse events leading to premature discontinuation of study drug will be tabulated by MedDRA SOC and PT for each treatment group, overall ABBV-8E12 dose groups, and all treatment groups combined. Treatment group differences between each ABBV-8E12 dose group and placebo will be analyzed using Fisher's exact test.

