11.3.3 Potentially Clinically Significant Laboratory Values

Criteria for potentially clinically significant (PCS) values have been predefined for selected laboratory variables as outlined in [Appendix A](#). For each variable, a summary of the number and percentage of subjects in each treatment group who have at least one double-blind observation that meets the PCS criteria and is more extreme than their baseline value will be provided. A listing will also be prepared that will include, for each variable, all observations for each subject that meet the PCS criteria for that variable at any time during the study. No comparisons of treatment groups will be performed.

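### The SAP drops the protocol's Fisher's exact tests of adverse events, each dose versus placebo, without itemising or justifying the change

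*SAP*

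**What the plan says.** Protocol 4.0 lists as one of two primary objectives: "To assess the long-term safety of ABBV-8E12 for up to 96 weeks in subjects with Early AD". SAP 4.1 repeats it.

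Protocol 8.1.6 sets the general rule. Each dose is compared with placebo, and comparisons are "performed with two-sided test at the significance level of 0.05, if applicable". Unless otherwise specified, "the treatment group differences in binary safety variables will be evaluated using a Fisher's exact test".

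Protocol 8.1.6.1 then names the test for adverse events: "Treatment group differences between each ABBV-8E12 dose group and placebo will be analyzed using Fisher's exact test". The sentence appears twice there, once for TEAEs and once for treatment-emergent serious events (including deaths) and adverse events leading to premature discontinuation of study drug. The synopsis has it too.

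The SAP says otherwise. In 11.2.1 the overview categories (any, related, severe, serious, leading to discontinuation, fatal, and all deaths) "will be summarized for each treatment group, ABBV-8E12 Overall. No comparisons of treatment groups will be performed". In 11.2.2 the incidence tables "will be summarized by primary SOC and PT for each treatment group, ABBV-8E12 Overall. No comparisons of treatment groups will be performed", and 11.2.2 also rules out comparisons in the tables by maximum severity and by relationship.

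**The concern.** The two documents give opposite instructions for the same outcomes, and those outcomes belong to a primary objective. Someone programming from the SAP would produce no estimate with uncertainty and no test of any dose against placebo for serious events, for discontinuations due to adverse events or for any event term. Someone reading the protocol would expect those tests in the report.

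The SAP is not avoiding safety inference in general. It keeps dose-versus-placebo ANOVA contrasts with P values and 95% intervals for laboratory, vital sign, weight and ECG mean changes (11.3.1, 11.4.1, 11.5.1). It also keeps Fisher's exact test for categorical baseline characteristics (7.1). Discontinuation due to an adverse event is not tested by another route either: Protocol 8.1.2 plans Fisher tests of premature discontinuation by reason, but SAP 8.0 names no test.

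**Working it through.** **Step 1. The documents side by side.**

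| Outcome | Protocol | SAP |
|---|---|---|
| TEAEs by system organ class (SOC) and preferred term (PT) | 8.1.6.1, synopsis: Fisher, each dose v placebo | 11.2.1, 11.2.2: no comparison |
| Treatment-emergent serious events | 8.1.6.1, synopsis: Fisher | 11.2.1, 11.2.2: no comparison |
| Adverse events leading to discontinuation | 8.1.6.1, synopsis: Fisher | 11.2.1, 11.2.2: no comparison |
| Severe TEAEs | No test of their own; general default in 8.1.6 | 11.2.1, 11.2.2: no comparison |
| Potentially clinically significant (PCS) values | 8.1.6.2 to 8.1.6.4: summary only; general default in 8.1.6 | 11.3.3, 11.4.2, 11.5.2: no comparison |
| Laboratory, vital sign and ECG mean changes | 8.1.6.2 to 8.1.6.4: ANOVA | 11.3.1, 11.4.1, 11.5.1: ANOVA, P values, 95% CIs |

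The first three rows contradict each other directly.

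**Step 2. Does version timing explain it?** SAP 3.0 says the plan was written against protocol Amendment 2, and the protocol in hand is later. Its list of changes (Appendix E) alters 8.1.7.1, 8.1.9, 8.1.10 and 8.3 within the statistical section. It does not touch 8.1.6.1, so the Fisher requirement was not introduced by the later amendment.

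**Step 3. Is the change declared?** SAP 14.0 says in general terms that changes from the protocol's planned analyses went into SAP version 1.0. It itemises only versions 2.0 and 3.0, and neither list mentions adverse event tests.

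**Step 4. What the missing inference would look like.** The plan gives no figure to reproduce here. Inputs: 100 per arm (Protocol 8.2) and two-sided 0.05 (Protocol 8.1.6). Event rates are assumptions, since the documents give none.

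Smallest active-arm count that reaches Fisher P ≤ 0.05 at 100 v 100:

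| Placebo | Active | P |
|---|---|---|
| 0 | 6 | 0.029 |
| 2 | 10 | 0.033 |
| 5 | 15 | 0.032 |
| 10 | 21 | 0.049 |
| 20 | 34 | 0.038 |

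Check by hand for 6 v 0: P = 2 × (100·99·98·97·96·95)/(200·199·198·197·196·195) = 2 × 0.01447 = 0.029. For 5 v 0 the same formula gives 2 × 0.02969 = 0.059, which misses.

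Half-width of a Wald 95% interval for a risk difference with a common rate p: 1.96 × √(2p(1−p)/100).

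- p = 5%: 1.96 × √0.00095 = 6.0 points
- p = 10%: 1.96 × √0.0018 = 8.3 points
- p = 20%: 1.96 × √0.0032 = 11.1 points

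Worked case, 15 v 5: the difference is 10 points and the half-width is 1.96 × √(0.15·0.85/100 + 0.05·0.95/100) = 1.96 × 0.0418 = 8.2. The interval is about 1.8 to 18.2 points.

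Exact power of the Fisher test under assumed true rates:

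| Placebo | Active | Power |
|---|---|---|
| 5% | 15% | 0.59 |
| 5% | 20% | 0.88 |
| 10% | 20% | 0.44 |
| 10% | 25% | 0.76 |

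A doubling from 10% to 20% would be missed more often than found. This is why an interval is worth having beside the P value.

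**The case against.** The best case for the SAP is that descriptive reporting of adverse events is defensible in a phase 2 trial. Three doses tested against placebo on every SOC and PT, without multiplicity control, produce many P values that are hard to interpret. Counts and percentages by arm are printed, so any reader can recompute a Fisher test or an interval. The protocol never asks for risk differences with intervals, and SAP 14.0 does disclose in general terms that it departs from the protocol.

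Much of that stands. Dropping the term-level tests could be a sound choice, and the risk difference with an interval is an addition to what the protocol specifies. But a general sentence does not say that these tests were dropped, or why, and nothing replaces them. The if-applicable qualifier in Protocol 8.1.6 does not help either, because 8.1.6.1 then names the test without qualification.

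Three stronger readings are tempting, and the documents do not support them.

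- A reader might infer that the safety objective is left with counts only. It is not: the overview, incidence and PCS tables give percentages by arm, and mean changes keep P values and intervals.
- A reader might infer that any later comparison of adverse events would be post hoc. The protocol prespecifies these tests, so running them would depart from the SAP but follow the protocol.
- A reader might treat PCS values as an equal contradiction. SAP 11.3.3 does say "No comparisons of treatment groups will be performed", but the protocol's own PCS paragraphs ask only for summaries. A PCS test rests solely on the general default in 8.1.6.

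**Conclusion.** The point holds for adverse events. The protocol requires two-sided Fisher's exact tests of each dose against placebo for TEAEs, treatment-emergent serious events and adverse events leading to discontinuation. SAP 11.2.1 and 11.2.2 drop them with no itemised reason and no substitute. The consequence is missing inference on part of a primary objective, not a biased result and not the loss of the objective.

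On size, at 100 per arm a split from 6 v 0 up to 34 v 20 would meet the protocol's own level and still be reported without a test or an interval. Typical interval half-widths would be 6 to 11 points. These figures assume the planned arm size and the event rates shown; they illustrate precision and do not predict results. The textual contradiction depends on none of them.

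**What to change.** In SAP 11.2.1, for any TEAE, severe TEAE, serious TEAE and TEAE leading to discontinuation of study drug, replace the sentence that rules out comparisons. The new text should give, for each dose versus placebo, the risk difference with 95% CI and the protocol's two-sided Fisher's exact P value, labelled nominal and unadjusted. Name the interval method, and choose one that behaves with zero counts.

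For the SOC and PT tables in SAP 11.2.2, do one of two things: restore the protocol's Fisher tests as nominal, or record and justify their removal in SAP 14.0 and align Protocol 8.1.6.1 and the synopsis.

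PCS comparisons are optional. While editing, resolve SAP 11.6.3, where the opening sentence says MRI safety findings will be compared with placebo and the closing sentence says they will not.

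The cost is SAP wording and a few table columns, with no new data. The downside is some additional nominal P values to interpret; limiting the required ones to the four overview categories keeps that small.

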Adverse events will be coded using the Medical Dictionary for Regulatory Activities (MedDRA). The number and percentage of subjects reporting treatment-emergent adverse events will be tabulated by MedDRA System Organ Class (SOC) and Preferred Term (PT) with a breakdown by treatment group. Tabulations will also be provided in which the number of subjects reporting an adverse event (MedDRA term) is additionally broken down by rating (mild, moderate or severe) and by whether possibly related to study drug. The number and percent of subjects experiencing treatment-emergent SAEs (including deaths) and adverse events leading to premature discontinuation of the study drug will be tabulated according to the MedDRA SOC and preferred term by treatment group. Treatment group differences between each ABBV-8E12 dose group and placebo will be analyzed using Fisher's exact test. Differences between each ABBV-8E12 dose group and placebo in change from baseline to minimum, maximum and final clinical laboratory evaluation, vital sign observation and ECG parameters will be analyzed by a one-way analysis of variance (ANOVA) with treatment as the main effect.

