6.1.3 Relationship to Study Drug

The investigator will use the following definitions to assess the relationship of the adverse event to the use of study drug:

Reasonable Possibility	An adverse event where there is evidence to suggest a causal relationship between the study drug and the adverse event.
-------------------------------	---

No Reasonable Possibility An adverse event where there is no evidence to suggest a causal relationship between the study drug and the adverse event.

For causality assessments, events assessed as having a reasonable possibility of being related to the study drug will be considered "associated." Events assessed as having no reasonable possibility of being related to study drug will be considered "not associated." In addition, when the investigator has not reported a causality or deemed it not assessable, AbbVie will consider the event associated.

[figure not shown]
If an investigator's opinion of no reasonable possibility of being related to study drug is given, an Other cause of event must be provided by the investigator for the serious adverse event.

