6.1.6 Toxicity Management

For the purpose of medical management, all adverse events and laboratory abnormalities that occur during the study must be evaluated by the investigator.

A drug-related toxicity is an adverse event or laboratory value outside of the reference range that is judged by the investigator or AbbVie as a "reasonable possibility" of being

related to the study drug (Section 6.1.3). A toxicity is deemed "clinically significant" based on the medical judgment of the investigator. The following guidelines should be used for study drug-related toxicity management.

Potential Drug-Related Toxicities

No potential drug related toxicities were identified from preclinical or clinical studies conducted to date. Examples of safety concerns that could be hypothetically associated with ABBV-8E12 and safety concerns associated with monoclonal antibodies, in general, are summarized below.

On-Target Toxicities

The brain appears to be the only organ to express tau at significant levels. Tau is an intracellular protein mainly expressed in neurons, although lower levels can be found in astrocytes and oligodendrocytes. ABBV-8E12 is directed against extracellular tau and no function of extracellular tau has been reported. No cellular uptake of mouse version of ABBV-8E12 antibody bound to tau aggregates was detected in preclinical studies.⁷ The likelihood of adverse on-target side effects of an anti tau immunotherapy is therefore anticipated to be low.

Non-Specific Off-Target Toxicities

Potential toxicities resulting from the non-human origin of ABBV-8E12 include allergic reactions or infusion reactions, including anaphylaxis or anaphylactoid reactions, flu-like symptoms, including fever, fatigue or loss of appetite, rash. ABBV-8E12 is lacking the Fc effector function activity and therefore Fc-mediated antibody-dependent cellular cytotoxicity and complement-dependent cytotoxicity is not expected. In addition, ABBV-8E12 exhibited a favorable in vitro immunosafety profile. No infusion reactions have occurred in the single dose PSP clinical study or the Expanded Access protocol.

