11.2.3 Listing of Adverse Events

The following additional summaries of adverse events will be prepared.

- List of subject numbers associated with each PT for all TEAEs
- List of subject numbers associated with each PT for all TEAEs assessed by the investigator as having Reasonable Possibility of Being Related.
- Listing of all serious adverse events
- Listing of all adverse events that led to discontinuation of study drug
- Listing of all fatal adverse events
- Listing of all deaths

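### The SAP's related-TEAE outputs do not apply the protocol rule that events with missing or unassessable causality count as associated, so they can fall below the protocol's count

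*SAP*

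**What the plan says.** Protocol 6.1.3 gives the investigator two levels, reasonable possibility and no reasonable possibility, and calls the first associated. It then sets a default for a gap in the assessment: "when the investigator has not reported a causality or deemed it not assessable, AbbVie will consider the event associated". Protocol 6.1.6 also lets either party establish relatedness, since a drug-related toxicity is one that "is judged by the investigator or AbbVie as a" reasonable possibility. For the tables, the protocol synopsis plans a breakdown "by whether possibly related to study drug" and mentions no third class.

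The SAP plans four outputs on relatedness:

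- Overview row (SAP 11.2.1): "Any TEAE that was rated as having reasonable possibility of being related to study drug by the investigator".
- SOC/PT table (SAP 11.2.2): "Any TEAE assessed by the investigator to have Reasonable Possibility of Being Related to study drug".
- Maximum-relationship table (SAP 11.2.2), with three categories: "Reasonable Possibility of Being Related, No Reasonable Possibility of Being Related and Unknown), as assessed by the investigator". Here, "If a subject has an adverse event with unknown relationship, then the subject will be counted in the relationship category of" unknown, unless another occurrence of the same event in that subject was rated as related.
- Subject list (SAP 11.2.3): "List of subject numbers associated with each PT for all TEAEs assessed by the investigator as having Reasonable Possibility of Being Related".

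The summary of changes in SAP 14.0 does not mention a departure from Protocol 6.1.3.

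**The concern.** Two stated rules give different answers for the same event. Under the protocol, an event with blank or unassessable causality is associated. In the SAP it is absent from the related overview row, the related SOC/PT table and the related subject list, and appears only under Unknown in the maximum-relationship table.

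Long-term safety is one of the two primary objectives, and SAP 11.2.1 and 11.2.2 plan no treatment comparisons on these outputs. A reader will therefore take the related rates at face value. If they rest on a less inclusive definition than the protocol's, and nothing says so, the reader cannot tell which definition was used. The discrepancy also runs one way only, towards fewer related events.

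**Working it through.** The documents state no figure on this point, so there is none to reproduce. The check compares the two rules and then scales the difference.

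**Classification of each event under the two rules**

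| Investigator's causality | Protocol 6.1.3 | SAP overview row, SOC/PT table, list | SAP maximum-relationship table |
|---|---|---|---|
| Reasonable possibility | Associated | Included | Related |
| No reasonable possibility | Not associated | Not included | Not related |
| Not reported or not assessable | Associated | Not included | Unknown |

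Only the last row differs. The SAP does not define Unknown. Placing unreported or unassessable causality there is an inference, but no other SAP category could hold such events.

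**Direction**

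Let R be the number of subjects in an arm with at least one TEAE rated a reasonable possibility. Let u be the number with at least one TEAE of unknown causality and none rated a reasonable possibility.

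- SAP related count = R
- Protocol related count = R + u
- Difference = u, which is zero or positive

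A subject who has both kinds of event is already in R and does not change the subject-level rate. At preferred-term level the same formula applies with R and u counted within the term.

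**Scale**

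The group size n is about 100 per arm (Protocol 8.2), hence 3 × 100 = 300 for the three active arms combined. The value of u is not in the documents, so the values below are assumptions. Shortfall in the related rate = u / n.

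| Assumed u in one arm | Shortfall, n = 100 |
|---|---|
| 0 | 0 points |
| 1 | 1 point |
| 2 | 2 points |
| 5 | 5 points |

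For the combined active group, each such subject adds 1/300, about 0.33 points.

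**What can be recovered from the planned tables**

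In the maximum-relationship table each subject is counted once per preferred term. Related plus Unknown therefore gives the protocol count for that term. The overall subject-level rate cannot be obtained by adding across terms, because one subject may contribute to several. The overview row, where that rate is reported, has no Unknown entry.

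**The case against.** The strongest reply is that two assessors are involved. Protocol 6.1.3 says how the sponsor will regard an event, in a section on assessing and reporting adverse events. The SAP outputs are labelled as the investigator's assessment and are accurate to that label. Protocol 8.1.6.1, the adverse event analysis section, neither repeats the default nor specifies a related-TEAE table. This stands as far as it goes, and it is why a silent recode under the present titles would be wrong: it would credit investigators with judgements they did not make. It does not explain why no planned output uses the protocol's classification, or why the difference is not stated.

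A second reply is that there may be few such events or none. Protocol 6.1 requires the investigator to record the relationship of each adverse event, the scale in 6.1.3 has no unknown option, and Protocol 10.2 has the case report forms reviewed for completeness. This stands, and it limits the size. The SAP nevertheless provides for unknown causality, so it allows that some will occur.

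A reader might also infer that the SAP treats unknown events as unrelated or hides them. The documents do not support that. Unknown is a separate category, it ranks above no reasonable possibility in the maximum-relationship table, and it is shown there by SOC and preferred term. All TEAEs are tabulated whatever their causality, and serious, fatal and discontinuation-causing events are also listed regardless of it.

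**Conclusion.** The conflict between Protocol 6.1.3 and SAP 11.2.1 to 11.2.3 is real but modest. Where a subject's only potentially related TEAE has missing or unassessable causality, the related overview row, SOC/PT table and subject list will count fewer subjects than the protocol's rule gives. The shortfall is 1 percentage point per such subject in an arm of 100. How many there will be is unknown, and the answer may be none. The conclusion assumes that the SAP's Unknown holds the events covered by the protocol's default.

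Two stronger conclusions are tempting. The first is that related-TEAE rates are understated as a matter of fact; the documents support only that they will be if such events occur. The second is that the comparison between arms is distorted. No test is planned on these outputs, the protocol rule would apply to placebo as well, and nothing in the documents shows that unknown causality would fall unevenly across arms.

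**What to change.** In the overview row (SAP 11.2.1), the related SOC/PT table (11.2.2) and the related subject list (11.2.3), count a TEAE with missing or unassessable causality as associated, citing Protocol 6.1.3. Retitle the three outputs so that the classification is not attributed to the investigator, and footnote the number of events classified by this rule. Keep the maximum-relationship table as the investigator's assessment with its Unknown column, so that the recorded data stay visible. State in the SAP that Unknown means causality not reported or not assessable.

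The cost is one derivation rule, new titles and a footnote. The related rate becomes slightly less favourable if any such events exist, and is unchanged if there are none.
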